Our objective is to determine if using Optison echocardiography contrast increases sensitivity and specificity of detecting left atrial appendage thrombus in transesophageal echocardiography studies as opposed to standard 2D and 3D TEE imaging without the use of echo contrast.

Study Population

Age of Participants: 18+

Sample Size:

At Utah: 500
All Centers: 500

Inclusion Criteria:

Patients referred to the University of Utah Echocardiography Lab for a transesophageal echocardiography (TEE) will be included in the study.

Subjects must be

- (1) > 18 years old
- (2) Able to provide consent
- (3) Indicated for TEE as a standard clinical procedure to evaluate cardiac health status

Exclusion Criteria:

- Patients will be excluded for meeting the contraindications for Optison administration.
1. Known right-to-left, or bi-directional cardiac shunts.
 2. Hypersensitivity to perflutren, blood, blood products or albumin.
 3. Women who pregnant (since Optison may have effects on the fetus that are currently unknown).
 4. Removal of Left Atrial Appendage.
 5. Not able to provide Informed Consent.

Design

Prospective Clinical Research

Study Procedures

Recruitment/Participant Identification Process:

Potential participants for the study will be recruited from the Cardiology/Electrophysiology (EP) clinic during normally scheduled clinic visits. No other recruitment procedures (phone call / recruitment letters) will be used in this study. In-person contact by the PI /sub-I or other cardiologists (made aware of study by word of mouth) who refer their patients into the study will be the primary mode of recruitment. Prior to approaching the subject, the PI/research staff will conduct a chart review to confirm that the potential subject fits the eligibility criteria for the study.

Potential participants will be screened by the PI/Co-PI and other cardiologists who are aware of the study and refer the subject to the study. When the patient is being seen in the clinic for a routine follow-up visit, if the patient fits with all the eligibility criteria during chart review (prior to clinician seeing the patient), then the PI/sub-I/ clinician will approach the potential participant and discuss the study with them.

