1. Patients will be identified and pre-screened using electronic medical records. Final screening and consent will be conducted in clinic, generally on the day that they were already scheduled to undergo a standard of care TEE for their specific clinical condition.
2. If the patient is found to be eligible based on inclusion/exclusion criteria, the investigator and/or study coordinator will approach them and explain the study.
3. If the patient agrees to participate and provides informed consent, then we fill out an enrollment sheet, create their study file and gather the necessary information from the patient.

4. Patient will then undergo their scheduled TEE without optison contrast. The clinician will determine whether it is possible to clearly identify the presence or absence of left atrial appendage thrombus from the standard TEE images.

5. If the presence or absence of thrombus cannot be clearly determined with standard TEE, the clinician will administer optison contrast and then continue the examination to try to obtain a conclusive result.

6. Data will then be collected, including ECHO reports, cardiac MRI reports, medical history, adverse events etc. as compiled during the procedure visit. Data will only be collected if the patient receives Optison during the TEE procedure.

7. Three months following the TEE, the medical record of the patients that received Optison will be reviewed for any additional adverse events or thrombii detection via other method. The end point of the study will be the collection of pertinent data, three months following TEE.

Statistical analysis will be conducted utilizing the statistical resources available to us through the CCTS.

Optison will be used for its approved indications (as an ultrasound contrast agent) and in compliance with the U.S. Food and Drug Administration (FDA) safety guidelines. Optison is a contrast agent used in ECHO studies, and does not involve any radiation/radioactive substances. The ECHO procedure does not expose patients to ionizing radiation, and Optison or ultra sound contrast agents do not contain dye or increase a patient's risk of nephrotoxicity. Ultrasound contrast agents are safe and completely radiation-free diagnostic imaging tools.

Procedures performed for research purposes only:

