Administration of Optison echocardiography contrast and re-imaging using standard 2 and 3D techniques will be the research-related procedure. The participant will be undergoing the Echocardiography for clinical indications and additional echo with optis contrast will be provided along with participant's clinical echo.

Statistical Methods, Data Analysis and Interpretation

Descriptive presentation of continuous variables and chi-squared / Fisher-exact tests for frequency variables. Since this study is a descriptive, pilot study to see utility of Optison in echocardiography, the contrast agent will be used in 100 patients to see at what

frequency the contrast agent is able to identify LAA thrombi. The contrast agent is already being used in echo, we are using it as it is approved by the FDA. A future larger RCT study will be construed using this pilot data.

While we intend to gather optison TEE data from 100 subjects, our enrollment cap has to be higher than that. Only those subjects whose standard TEE's are inconclusive will be administered optison, and subjects will need to be consented prior to the start of the standard TEE. Because only a minority of enrolled patients will receive optison, we plan to enroll 500 patients.

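### Study data are kept only for Optison recipients, so standard TEE's thrombus detection yield, and the relative gain in detected thrombi from adding Optison, cannot be computed

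*Combined protocol and SAP*

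**What the plan says.** The objective sets Optison-enhanced TEE against its comparator, "as opposed to standard 2D and 3D TEE imaging without the use of echo contrast", in terms of sensitivity and specificity for LAA thrombus.

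The Procedures list then runs as follows.

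- **Step 1.** Patients are generally consented on the day "they were already scheduled to undergo a standard of care TEE for their specific clinical condition", so the TEE itself is clinical care.
- **Step 3.** After consent, "we fill out an enrollment sheet, create their study file and gather the necessary information from the patient". This applies to every consented patient but comes before the TEE.
- **Step 4.** In every patient the clinician decides whether it is possible to "clearly identify the presence or absence of left atrial appendage thrombus from the standard TEE images".
- **Step 5.** If it is not, Optison is given, to "continue the examination to try to obtain a conclusive result".
- **Step 6.** "Data will only be collected if the patient receives Optison during the TEE procedure".
- **Step 7.** The three-month record review covers the same recipients only.

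The section on statistical methods confirms the selection: "Only those subjects whose standard TEE's are inconclusive will be administered optison". It aims for Optison data from 100 patients, to describe how often contrast identifies LAA thrombi, and says a future larger RCT will be based on this pilot. On enrolment it says: "Because only a minority of enrolled patients will receive optison, we plan to enroll 500 patients".

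**The concern.** Steps 4 to 6 together mean that a standard TEE enters the dataset only if it was inconclusive. The studies in which standard TEE clearly showed or excluded a thrombus stay in the clinical record and are not taken into the study. The dataset therefore holds no definite standard read against which to set Optison's yield, although the objective is framed as a comparison with non-contrast TEE.

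The number of thrombi found after Optison is hard to interpret on its own. The same count could be most of the thrombi found in the enrolled population or a small part of them. That distinction also matters for planning the later RCT, for which the detection yield of standard TEE is an obvious input.

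**Working it through.** **Inputs from the plan.** Enrolment cap 500; target Optison recipients 100; Optison only after an inconclusive standard TEE; data only from Optison recipients. The plan states no inconclusive rate and no thrombus rate. The 500 therefore cannot be rebuilt independently: 100/500 = 20% is the inconclusive rate it implies, and 100/0.20 = 500 only returns the input.

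**Reads not abstracted.** 500 − 100 = 400, and 400/500 = 80%. This is implied, not stated. If the inconclusive rate is f, the share not abstracted is 1 − f:

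| Assumed f | Share not abstracted |
|---|---|
| 10% | 90% |
| 20% (implied) | 80% |
| 30% | 70% |
| 40% | 60% |

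The plan says only a minority will receive Optison (f below 50%), so the share exceeds 50% in any case.

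**What can and cannot be computed.** Let N be the number enrolled, x the thrombi found after Optison, and T the thrombi found on conclusive standard TEEs.

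- Yield among inconclusive studies, x/100: available.
- Inconclusive rate, 100/N, and absolute added yield, x/N: available if N is reported.
- Rate of conclusive results before and after Optison: available if N is reported. If Optison resolves an assumed 80 of 100, it rises from 400/500 = 80% to 480/500 = 96%.
- Standard TEE yield, T/N: not available, because T is not collected.
- Relative gain in detected thrombi, x/T: not available.
- Share of detected thrombi found only after Optison, x/(x + T): not available.

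On the planned data T could lie anywhere from 0 to 400, so T/N is bounded only by 0% and 400/500 = 80%, and x/T has no upper bound.

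**Illustration.** Assume x = 10 and N = 500. The absolute added yield is 10/500 = 2.0% (exact 95% CI 1.0% to 3.6%) whatever the other 400 reads show. With assumed values of T:

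| T among 400 | Standard yield T/500 | Combined yield (T + 10)/500 | Relative gain 10/T | Share found only after Optison, 10/(10 + T) (exact 95% CI) |
|---|---|---|---|---|
| 4 | 0.8% | 2.8% | 250% | 10/14 = 71% (42% to 92%) |
| 20 | 4.0% | 6.0% | 50% | 10/30 = 33% (17% to 53%) |
| 40 | 8.0% | 10.0% | 25% | 10/50 = 20% (10% to 34%) |

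All three rows give the same planned dataset. If T were recorded, the first and last rows would have non-overlapping intervals. The middle row overlaps both, so at pilot size the extra field separates extremes but not every case.

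**The case against.** The strongest reply is that the restriction is a consistent choice of scope. Steps 5 to 7 and the statistical section all confine the study to inconclusive TEEs, because the pilot asks what contrast adds when standard imaging fails. No section names a standard-TEE detection rate or a relative gain in detected thrombi as a target. The pilot aim is met without them, and recording them would not deliver the sensitivity and specificity named in the objective. That is right, and it keeps this point at the level of a cheap improvement. It does not remove the point: the objective is still a comparison with non-contrast TEE, and the pilot is meant to feed an RCT.

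A second reply is that the resulting yields would be hard to interpret. They depend on the mix of referrals, positives are unverified, and the clinician calls a read conclusive knowing that Optison is available. This also stands. Recording the indication describes the referral mix but does not cure the rest, so the yields must be labelled as unverified.

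A third is that the size rests on assumed counts and that 500 is a cap, so recruitment might stop earlier. True; the 400 is an implied figure and the table is an illustration. The loss of T does not depend on either.

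Finally, the low cost is not fully verifiable. The consent pages are not available for this review, and the plan does not say that every clinical report carries a codable LAA result. Both need checking before the change is made.

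**Conclusion.** The concern holds. Under step 6, the apparent thrombus detection yield of standard TEE and the relative gain in detected thrombi from conditional Optison cannot be computed from the planned data. The results left out belong to an implied 400 of 500 patients (80%), and to more than half of those enrolled at any inconclusive rate consistent with the plan. No other section overrides the rule, and the information gathered in step 3 comes before the TEE, so it provides for no TEE result.

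The finding is limited. Optison's yield among inconclusive studies is unaffected. The inconclusive rate, the absolute added yield and the rise in conclusive results all survive if the number enrolled is reported. The 80% assumes that the target of 100 and the cap of 500 are both met exactly. The relative gains of 25% to 250% rest on assumed counts and show only how far the answer can move. This is a cheap improvement, not a defect in the pilot aim.

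**What to change.** Amend step 6 so that, for every consented patient who has the TEE, the study records the standard-TEE LAA result (present, absent or inconclusive) and the TEE indication. The fuller data collection and the three-month review can stay limited to Optison recipients.

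Add to the statistical section:

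- the number enrolled and the inconclusive rate with its exact CI (100/500 would be 20%, 95% CI 16.6% to 23.8%);
- the apparent detection yield of standard TEE alone and of standard TEE plus conditional Optison, with the absolute and relative gain;
- the share of detected thrombi found only after Optison, with its exact CI.

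Label these as unverified detection yields. They are not sensitivity or specificity, because no reference standard is defined and patients with conclusive reads receive no Optison.

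The cost is abstracting one or two fields from the clinical TEE report for up to about 400 already-consented patients, and confirming that the consent covers it and that the report gives a codable result. No new procedure, visit, patient or follow-up review is needed.

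### The stated objective, a gain in sensitivity and specificity over standard TEE, cannot be estimated from this design; the planned detection frequency answers a narrower question

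*Combined protocol and SAP*

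**What the plan says.** - **Opening objective statement.** The aim is to learn whether Optison "increases sensitivity and specificity of detecting left atrial appendage thrombus", with 2D and 3D TEE without contrast as the comparator.
- **Procedures, steps 4 and 5.** Every patient has a standard TEE first. Only if it is unclear does contrast follow: "the clinician will administer optison contrast and then continue the examination to try to obtain a conclusive result". No rule is given for studies that remain unclear after contrast.
- **Procedures, step 6.** The data listed include echo reports and "cardiac MRI reports, medical history, adverse events etc. as compiled during the procedure visit". The step then limits collection: "Data will only be collected if the patient receives Optison during the TEE procedure".
- **Procedures, step 7.** At three months, "the medical record of the patients that received Optison will be reviewed for any additional adverse events or thrombii detection via other method". The other method is not named.
- **Statistical Methods, Data Analysis and Interpretation.** "Since this study is a descriptive, pilot study to see utility of Optison in echocardiography, the contrast agent will be used in 100 patients", and the quantity of interest is the "frequency the contrast agent is able to identify LAA thrombi". Chi-squared or Fisher exact tests are planned for categorical variables, without saying which groups are compared. The section repeats the selection rule: "Only those subjects whose standard TEE's are inconclusive will be administered optison". Sensitivity and specificity are not mentioned there.

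**The concern.** Sensitivity and specificity need two things: a definite reading from each test and an independent determination of whether thrombus was present. A comparison of two tests needs both for each test. The design keeps only patients in whom the comparator gave no definite reading, and it designates no method for establishing the truth. The analysis section plans a different quantity from the one in the objective.

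The statistical section also says that a larger randomised trial will be built on these data. If the pilot is reported under its present objective, a detection frequency may be read as evidence of improved accuracy and carried into that trial's design.

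A smaller, related gap lies in step 7. It looks for thrombi found by another method but does not specify recording that a patient was re-imaged and clear, or was never re-imaged. Data collected to that specification may not separate the two.

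**Working it through.** **1. The plan's own figures.** It gives 500 enrolled and 100 with contrast, so 100/500 = 20% are implicitly expected to have an inconclusive standard TEE. The text says only that they are a minority. No alpha, power, effect size or precision target is stated, so there is no sample-size calculation to reproduce.

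**2. The comparator.** Sensitivity = TP/(TP + FN) and specificity = TN/(TN + FP). Each cell requires a positive or negative reading. By steps 4 to 6, standard TEE is inconclusive in 100 of 100 contrast patients, so none of its four cells can be filled. Patients with a clear standard TEE receive no contrast, so they cannot supply the paired comparison either. More patients, or a perfect reference standard, would not change this.

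**3. The planned quantity.** If every contrast study is conclusive, detection frequency = p × Se + (1 − p) × (1 − Sp), where p is thrombus prevalence. The documents give no p. Suppose 10 detections in 100, under three assumed prevalences:

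| Assumed p | One consistent reading of 10/100 |
|---|---|
| 5% | all 5 thrombi found, 5 false positives: Se 100%, Sp 90/95 = 94.7% |
| 10% | all 10 found, no false positives: Se 100%, Sp 100% |
| 20% | 10 of 20 found, no false positives: Se 50%, Sp 100% |

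The same frequency fits quite different accuracies, so it identifies neither measure.

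**4. What the step 7 gap could do if accuracy were computed anyway.** This is illustration only, because the plan proposes no such analysis and every input is assumed. Take n = 100, p = 10%, Se 80%, Sp 95%: TP 8, FN 2, FP 4.5, TN 85.5. Contrast-positives number 12.5 and contrast-negatives 87.5.

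| Who is re-imaged | Rule | Apparent Se | Apparent Sp |
|---|---|---|---|
| 50% of positives and 50% of negatives, depending on contrast result alone | re-imaged only | 4/(4 + 1) = 80% | 42.75/(42.75 + 2.25) = 95% |
| Same patients | no charted detection counted as no thrombus | 4/(4 + 1) = 80% | (85.5 + 1)/(85.5 + 1 + 4.5 + 4) = 91% |
| 50%/50%, but 1.5 of the 2 FN re-imaged | re-imaged only | 4/(4 + 1.5) = 73% | 42.25/(42.25 + 2.25) = 95% |
| 80%/20%, depending on contrast result alone | re-imaged only | 6.4/(6.4 + 0.4) = 94% | 17.1/(17.1 + 3.6) = 83% |
| 80%/20%, but 1.6 of the 2 FN re-imaged | re-imaged only | 6.4/(6.4 + 1.6) = 80% | 15.9/(15.9 + 3.6) = 82% |

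In rows 3 and 5 the re-imaged true negatives are the remainder: 43.75 − 1.5 = 42.25 and 17.5 − 1.6 = 15.9. Rows 1 and 2 show that the same charts give different specificities depending on how a patient never re-imaged is treated. Rows 1 and 3 show that equal re-imaging rates do not guarantee absence of bias. Rows 4 and 5 show that unequal rates do not always push sensitivity up. The direction cannot be stated in advance.

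**5. What the design can estimate.** Exact (Clopper-Pearson) 95% limits for x of n are the 2.5% quantile of Beta(x, n − x + 1) and the 97.5% quantile of Beta(x + 1, n − x). At n = 100:

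| Count | 95% CI |
|---|---|
| 5 | 1.6 to 11.3% |
| 10 | 4.9 to 17.6% |
| 20 | 12.7 to 29.2% |
| 80 | 70.8 to 87.3% |
| 90 | 82.4 to 95.1% |

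**The case against.** The strongest reply is that this is a self-described descriptive pilot whose statistical section promises a frequency and computes no accuracy measure, so no biased estimate is planned. That stands, and it is why the illustration in working step 4 is not a predicted error. The pilot label explains the missing power calculation. It does not bring the objective into line with the analysis.

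The records may also hold more than step 7 spells out. Echo and cardiac MRI reports are collected in step 6 and could carry negative findings, and step 7 ends with an undefined reference to relevant data. This stands in part. The MRI reports are limited to those from the procedure visit, are not required for every patient and are not designated as the reference. Step 3 opens a study file for every consenting patient, which sits awkwardly with step 6, but it supplies neither a contrast reading nor a reference standard for the others. The categorical tests are planned too, yet with no groups or accuracy measure attached.

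Three stronger readings are tempting and not supported:

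- A reader might infer that sensitivity will be inflated and specificity deflated. That requires positives to be re-imaged more often, and re-imaging to depend on the contrast result alone. The documents say neither.
- A reader might infer that early and late detections will be pooled, or negative findings discarded. Step 7 is silent on both, and silence is not a rule.
- A reader might put a number on the gain over standard TEE by coding inconclusive readings as positive or negative. No part of the plan proposes such coding.

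**Conclusion.** The point holds as a mismatch between the objective and what the design and analysis can deliver. The central fact is structural and needs no assumed input: none of the 100 intended contrast patients has a definite standard TEE reading, no reference standard is named, and the planned frequency identifies neither sensitivity nor specificity.

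The step 7 gap is secondary. It matters only if accuracy is later computed, and then the size and direction of any bias depend on who is re-imaged, which the documents leave open.

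The narrower question, what contrast yields after an inconclusive TEE, is answerable with 100 patients. The widest of the intervals tabulated runs from 12.7 to 29.2%. This should be put right before the pilot is reported or used to plan the later trial; it is no reason to abandon the pilot.

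**What to change.** 1. **Reconcile the objective with the statistical section.** Restate the pilot objective as follows: in patients with an inconclusive standard TEE, estimate the frequency of conclusive results and the frequency of thrombus detections with Optison, each with an exact 95% confidence interval. Keep studies that remain unclear after contrast in the denominator. Make no claim of a gain in sensitivity or specificity over standard TEE.
2. **Specify the step 7 abstraction.** In the chart review already planned, record date, method and result (positive, negative, not done) for any other imaging of the appendage. Report how many patients were verified, separately by contrast result. Do not count unverified patients as true negatives or as false positives.

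The cost is a change of wording, slightly more abstraction and a more modest objective. No new imaging and no additional patients are needed. The comparison of accuracy with standard TEE is left to the later trial.

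### The only diagnostic measure named in the statistics section counts thrombi found and, as worded, does not separate patients cleared of thrombus from patients still inconclusive after contrast

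*Combined protocol and SAP*

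**What the plan says.** The combined document states its objective in the opening paragraph: to find out whether contrast "increases sensitivity and specificity of detecting left atrial appendage thrombus".

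Under Study Procedures, Procedures, step 4, the clinician first judges from the standard TEE whether it is possible to "clearly identify the presence or absence of left atrial appendage thrombus". Under step 5, when that is not possible, contrast is given so as to "continue the examination to try to obtain a conclusive result". The section on Statistical Methods, Data Analysis and Interpretation confirms who receives it: "Only those subjects whose standard TEE's are inconclusive will be administered optison".

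The same section names one diagnostic quantity: "the contrast agent will be used in 100 patients to see at what" "frequency the contrast agent is able to identify LAA thrombi". The remaining analysis text is general: description of continuous variables, and chi-squared or Fisher tests for frequency variables that are not named. The section calls the study a descriptive pilot on the utility of the agent and says that a later, larger RCT will draw on its data.

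Step 6 collects data on contrast patients, "including ECHO reports, cardiac MRI reports, medical history, adverse events etc. as compiled during the procedure visit". Step 7 reviews their records at three months for "any additional adverse events or thrombii detection via other method".

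The document does not define *identify* or *conclusive*. It also does not say how negative or still-inconclusive contrast studies are counted, and it names no proportion of inconclusive studies resolved.

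**The concern.** A contrast study under step 5 can end in three ways: thrombus seen, thrombus excluded, or still not settled. The third is a real possibility, because step 5 speaks only of trying for a conclusive result. The named measure counts the first outcome and leaves the other two together in the remainder.

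Those two are opposites for the purpose for which contrast is given. Excluding a thrombus after an inconclusive study is a success under steps 4 and 5, and a study that stays inconclusive is a failure. A pilot reported on the named measure alone would show how many thrombi were found after an inconclusive TEE, but not how often contrast did what step 5 asks of it. The designers of the later RCT would then lack a resolution rate from the pilot, or would have to build one afterwards without an agreed definition of *conclusive*.

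**Working it through.** **The plan's own figures.** The statistics section gives 100 contrast patients and 500 enrolled. The implied share is 100/500 = 20%, which agrees with its remark that a minority will receive contrast. It states no expected rate, precision target, alpha or power, so the 100 cannot be derived, and no stated number is shown to be wrong. The check therefore concerns what the named measure can distinguish at n = 100.

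**Inputs.** From the documents: n = 100 contrast patients, all with an inconclusive standard TEE. Assumed, because the documents give no rates: the number of patients in each outcome.

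**Formulas.** Let P, A and I be the numbers of contrast patients with thrombus present, thrombus absent and still inconclusive, with P + A + I = 100.

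- Named measure, as worded: P/100. Its complement is (A + I)/100, undivided.
- Share made conclusive: (P + A)/100.
- Exact (Clopper-Pearson) 95% interval for x of n: the lower limit is the 2.5% quantile of Beta(x, n − x + 1), and the upper limit is the 97.5% quantile of Beta(x + 1, n − x).

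**Results.**

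| P / A / I (assumed) | Named measure (95% CI) | Share conclusive (95% CI) |
|---|---|---|
| 10 / 80 / 10 | 10% (4.9–17.6) | 90% (82.4–95.1) |
| 10 / 45 / 45 | 10% (4.9–17.6) | 55% (44.7–65.0) |
| 10 / 10 / 80 | 10% (4.9–17.6) | 20% (12.7–29.2) |
| 5 / 90 / 5 | 5% (1.6–11.3) | 95% (88.7–98.4) |
| 5 / 5 / 90 | 5% (1.6–11.3) | 10% (4.9–17.6) |

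Within the first three rows the named measure and its interval are identical, while the share made conclusive runs from 20% to 90%. The last two rows show the same with 5 thrombi. In general, for a given P the share made conclusive can lie anywhere from P/100 (nobody else cleared) to 100% (everybody else cleared), and the named measure does not move.

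**Precision of the missing proportion.** The planned 100 contrast patients would estimate it usefully. If 80 of 100 became conclusive, the exact 95% CI is 70.8–87.3% (Wilson 71.1–86.7%).

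**The case against.** The strongest reply is that one informal sentence is being read too literally. Step 4 uses the same verb, *identify*, for the two-sided question, and step 5 gives the aim as a conclusive result. Read with those steps, the phrase in the statistics section could be shorthand for settling the question either way. That is possible. But step 4 spells out both sides where both are meant, and the statistics section does not, so the reading is left open.

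A second reply is that nothing in the plan prevents a three-way report. The study is descriptive, frequency variables are foreseen, and step 6 collects the echo reports of contrast patients. This also stands: the gap is in the definition of the outcome and probably not in the data. One might go further and say that the split would have to be extracted from free text. The documents do not say whether the reports are free text or structured, so that cannot be claimed. What can be said is that *conclusive* has no definition set in advance.

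A third reply is that the stated objective is sensitivity and specificity, not resolution. That is true, and a resolution proportion estimates neither. The statistics section, however, names neither of them, and resolution is the purpose that step 5 itself gives for contrast.

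A reader might also infer that the named measure says nothing about utility. That goes too far. Every contrast patient had an inconclusive standard TEE, so each thrombus then found is itself one form of utility. Nor do the documents support the inference that false positives would dominate the count. They give no prevalence or accuracy figures, the result would depend wholly on assumed ones, and accuracy is a separate question from pooling cleared patients with unresolved ones.

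**Conclusion.** The point holds as a gap in the outcome definition. As worded, the only diagnostic measure named in the statistics section counts positive reads and pools patients cleared of thrombus with patients still inconclusive, although contrast is given to settle the question in either direction. The measure is incomplete, not uninformative.

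The size is illustrative. With an assumed 10 of 100 identified, the reported figure is the same whether contrast settled one in five of the inconclusive studies or nine in ten. The conclusion rests on reading the phrase as it is written. If the sponsor meant it as shorthand for presence or absence, the defect reduces to one clarifying sentence and a definition of *conclusive*.

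This is a cheap improvement. Its main justification is that a later RCT is to draw on these data.

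**What to change.** In Statistical Methods, Data Analysis and Interpretation:

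- Define *conclusive* before data are read, and say what *identify* means. If the phrase was meant to cover both presence and absence, say so.
- Record each post-contrast read as thrombus present, thrombus absent or still inconclusive, and report all three counts.
- Report the proportion of inconclusive standard TEEs that became conclusive after contrast, with an exact or Wilson 95% CI. Keep the thrombus-found frequency alongside it.
- State that this proportion does not estimate the sensitivity and specificity named in the objective, and that a conclusive read is not necessarily a correct one.
- Later imaging found in the cardiac MRI reports (step 6) or the three-month review (step 7) may be listed descriptively with its date. Reads should not be labelled as contradicted on that basis. The plan gives no time window or adjudication rule for such a label, and thrombus status may change over three months.

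The cost is one data-form field, one definition and one extra proportion. No new visit, imaging or patients are needed. The change does not supply a reference standard.
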